6.9 EARLY STOPPING OF FOLLOW-UP

The trial will distinguish between stopping of trial treatment and stopping of trial follow-up. Whilst stopping trial follow-up requires stopping trial treatment if the child is still receiving antibiotics as randomised, stopping trial treatment does not necessarily mean that the child automatically has to stop trial follow-up. **The parent/carers wishes with respect to trial treatment and trial follow-up should be respected at all times.** If a parent/carer who chooses to discontinue trial treatment for their child remains happy to follow the other trial procedures and follow-up schedule, their child may remain in the trial **"on-study, off-study-treatment"**. However, if they do not wish to remain on trial follow-up, their decision must be respected and the child will be withdrawn from trial follow-up. The CTU should be informed of this in writing using the appropriate documentation. Prior to transferring to routine follow-up, the parent/carer will be asked whether they would be happy for their child to have assessments performed as for the final study visit. They would be at liberty to refuse any or all individual components of the follow-up assessments and their wishes should be respected.

If follow-up is stopped early, the anonymised medical data collected during their participation in the trial will be kept and used in the analysis; consent cannot be withdrawn for the use of historical anonymised data already collected. Consent may be withdrawn at the discretion of the parent/carer for the future use of any stored samples.

Given the short follow-up period (28 days), children who have left the trial may not re-consent to participation in the trial at a subsequent hospitalisation episode.

Children who stop trial follow-up early will not be replaced, since the sample size calculation already incorporates an inflation factor to account for lost-to-follow-up.

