9.3 SAMPLE SIZE

9.3.1 MAIN TRIAL (PEDI CAP-A)

1,000 children randomised 1:1 to oral step-down with amoxicillin vs co-amoxiclav provides >80% power to detect a 6% absolute reduction (corresponding to a 40% relative reduction) in 28-day re-admission or mortality (all-cause) from 15% (amoxicillin) to 9% (co-amoxiclav) assuming 5% lost-to-follow-up at 28-days post-randomisation (two-sided $\alpha=0.05$).

Randomizing 500 children between 5 equidistant duration groups for amoxicillin and for co-amoxiclav is sufficient to estimate the duration response curve within a 5% error margin in >95% of simulations [33].

For comparison of the co-amoxiclav step-down with the 5-day intravenous groups, randomising 500 vs 100 children respectively provides 89% power to demonstrate non-inferiority based on a 10% non-inferiority margin for a 9% failure rate (two-sided $\alpha=0.05$) (power is >80% for failure rates up to 12%). A 10% non-inferiority margin has been recommended by the United States (US) Food and Drug Administration (FDA) for adult bacterial CAP based on similar hypothesised event rates with and without antibiotics to those observed in children [53].

Therefore the total sample size for the main trial (PediCAP-A) is 1,100 (including the additional 5-day intravenous group). There is no formal adjustment for non-compliance because the trial is pragmatic, designed to evaluate the impact of strategic approaches to antibiotic choice and duration. Rather, non-compliance is a separate secondary outcome (incorporating change from allocated antibiotic regimen for any reason) which will be analysed separately, and the results of the primary analysis interpreted conditional on this.

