9.5 ANALYSIS PLAN (BRIEF)

The analyses will be described in detail in a full Statistical Analysis Plan. This section briefly summarises the main issues.

The primary analysis population is intention-to-treat, including all randomised children, regardless of treatment received. This corresponds to estimating the impact of the effectiveness of the strategies of stepping down to oral amoxicillin vs co-amoxiclav and varying total duration of antibiotics. However, in secondary analyses we will also use inverse-probability weighting methods to adjust for deviation from randomised strategy, both duration of antibiotic treatment and oral-stepdown, which is a more efficient approach than defining a per-protocol population [55].

As follow-up is short (28 days post-randomisation) lost-to-follow-up should be low, and in each population, the primary comparison between randomised groups will be conducted using binomial regression, reported on the risk difference scale (following the sample size calculation which is based on risk differences). The primary analysis will adjust for the randomisation stratification factors (site and the other factorial randomisation). The primary analysis will be conducted on observed data. Secondary analyses will use multiple imputation with chained estimating equations to impute outcomes for the small (5%) number of expected missing outcomes due to losses to follow-up before 28 days post-randomisation (the sample size calculation in [Section 9.3](#) includes an inflation factor to allow for this). Imputation will be done separately within each randomised group to allow for unknown interactions, and will be based on outcomes and main baseline characteristics as recommended. Duration-response curves will be estimated separately for oral amoxicillin and oral co-amoxiclav randomised groups using fractional polynomials to flexibly model the impact of duration on response following Quartagno et al [33]. A combined model will test whether there is evidence that these duration-response curves vary between co-amoxiclav and amoxicillin using main effects and interactions (i.e. subgroup effects), specifically the following key factors:

- site

- severity
- age
- HIV infection and exposure
- malnutrition (assessed by weight-for-height Z-scores, according to the WHO Growth Standards, and pedal oedema/MUAC)

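### The non-inferiority power in Protocol 9.3.1 reproduces only without loss to follow-up, although 6.9 and 9.5 say loss is already allowed for; the gap is about 2 points

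*Protocol*

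**What the plan says.** Section 9.3.1 of the Protocol makes two power statements for the main trial.

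- **Superiority, amoxicillin vs co-amoxiclav.** More than 80% power for 15% vs 9% with 1,000 children, "assuming 5% lost-to-follow-up at 28-days post-randomisation".
- **Non-inferiority, co-amoxiclav step-down vs 5-day intravenous.** Here "randomising 500 vs 100 children respectively provides 89% power to demonstrate non-inferiority", "based on a 10% non-inferiority margin for a 9% failure rate", at two-sided alpha 0.05. A parenthesis adds that "power is >80% for failure rates up to 12" per cent. Loss to follow-up is not mentioned in this sentence.

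Two later sections describe the calculation as already covering loss. Section 6.9 does not replace children who stop follow-up early, because "the sample size calculation already incorporates an inflation factor to account for lost-to-follow-up". Section 9.5 expects 5% of outcomes to be missing, says the calculation in Section 9.3 "includes an inflation factor to allow for this", and bases the primary analysis on observed data.

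**The concern.** Sections 6.9 and 9.5 are not limited to one comparison. A reader will take the 89% and the 12% tolerance as figures that hold after 5% loss. Yet the non-inferiority sentence names the randomised numbers and states no loss. If its figures were computed on complete follow-up, they rest on a basis that the other two sections say is not used.

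What is at stake is limited but real. The intravenous group is the smallest comparator in the trial, lost children are not replaced, and the 12% parenthesis tells the reader how far the failure rate can rise before power becomes inadequate. Section 9.3.1 itself plans for 15% failure on amoxicillin, so failure rates near 12% are not remote from the protocol's own assumptions.

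**Working it through.** **Inputs.** From 9.3.1: 500 vs 100 randomised, margin 0.10, failure rates 9% and 12%, two-sided alpha 0.05 (z = 1.96). From 9.3.1 and 9.5: 5% loss. Assumptions made here: the true failure rate is equal in both groups, and loss is equal in both groups, which gives 500 × 0.95 = 475 and 100 × 0.95 = 95.

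**Formula** (unpooled normal approximation; the protocol names no method):

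SE = √[p(1−p)(1/n₁ + 1/n₂)], power = Φ(0.10/SE − 1.96)

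**Step 1. Reproduce the stated figures on 500 vs 100** (1/500 + 1/100 = 0.01200).

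- p = 0.09: SE = √(0.0819 × 0.01200) = 0.03135; 0.10/SE = 3.190; Φ(1.230) = 89.1%.
- p = 0.12: SE = √(0.1056 × 0.01200) = 0.03560; 0.10/SE = 2.809; Φ(0.849) = 80.2%.
- 80% power needs 0.10/SE = 1.960 + 0.842 = 2.802, so p(1−p) = 0.01/(2.802² × 0.01200) = 0.1062 and p = 12.1%.

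Both stated figures, and the stopping point at 12%, are matched with no loss.

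**Step 2. Same formula on 475 vs 95** (1/475 + 1/95 = 0.01263).

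- p = 0.09: SE = 0.03216; 0.10/SE = 3.109; Φ(1.149) = 87.5%.
- p = 0.11: SE = 0.03517; 0.10/SE = 2.844; Φ(0.884) = 81.2%.
- p = 0.12: SE = 0.03652; 0.10/SE = 2.738; Φ(0.778) = 78.2%.
- 80% limit: p(1−p) = 0.01/(2.802² × 0.01263) = 0.1009, so p = 11.4%.

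The 12% figure has almost no slack: 1% loss (495 vs 99) already gives 79.8%.

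**Step 3. Check the superiority sentence.** On 475 per group, SE = √[(0.15 × 0.85 + 0.09 × 0.91)/475] = 0.02100; 0.06/SE = 2.858; Φ(0.898) = 81.5%. That claim of more than 80% survives the loss it states, so the mismatch is confined to the non-inferiority sentence.

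**Step 4. Could another method give the stated figures on 475 vs 95?**

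| Method, 475 vs 95 | Power at 9% | Power at 12% |
|---|---|---|
| Stated in 9.3.1 | 89% | >80% |
| Unpooled normal | 87.5% | 78.2% |
| Unpooled normal, continuity corrected | 83.0% | 72.8% |
| Exact power, Wald limit | 93.7% | 83.3% |
| Farrington-Manning | 95.1% | 88.7% |
| Exact power, Newcombe limit | 97.4% | 91.0% |

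None of these, at the stated alpha, gives 89% at 9% failure together with an 80% limit at 12%. One-sided 0.05 with continuity correction comes closest (89.8% and 82.1%), but it contradicts the stated alpha and moves the 80% limit to nearly 13%. No loss with the unpooled approximation is therefore the natural reading.

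**The case against.** The strongest reply is that the sentence is correct as written: it names 500 vs 100, its figures reproduce on those numbers, and it claims no loss allowance. Sections 6.9 and 9.5 speak of the calculation in the singular, which could mean the superiority calculation, a co-primary objective that does carry 5% loss. Section 1.4.3 calls the intravenous arm a benchmark and not a formal control, and sections 6.10 and 9.2.4 describe active tracing to keep loss low.

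Much of this stands. There is no arithmetic slip inside the sentence, and the effect is small. What does not stand is confining the later statements to one comparison. Both are worded generally, 9.5 points to Section 9.3 as a whole, and 9.3.1 gives the intravenous comparison a formal margin, alpha and power, which it then uses to arrive at 1,100 children.

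A reader might go further and infer that the comparison is underpowered, or that the 12% tolerance fails by the protocol's own formula. The documents do not support either. No formula is named, and the shortfall appears under the approximation that reproduces the stated figures (and its continuity-corrected form). Exact power of the Wald limit with 5% loss is still 83.3% at 12% failure and 81.5% at 12.5%. This is not bought with a loose test: at a true difference of 10 points and intravenous failure rates of 9% to 13%, its one-sided error on 475 vs 95 is about 1.5% to 1.6%, below 2.5%.

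**Conclusion.** The point holds as a minor correction of a stated figure. The quoted non-inferiority power is a no-loss figure, while sections 6.9 and 9.5 tell the reader that loss is already in the calculation. On the approximation that reproduces it, allowing for 5% loss lowers power by 1.6 points at 9% failure (89.1% to 87.5%) and by 2.0 points at 12% (80.2% to 78.2%), and moves the 80% limit from 12.1% to 11.4% failure.

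This rests on three assumptions: 5% loss equal in both groups, equal true failure rates, and the inference that the unpooled normal approximation was used. It changes no sample size, margin or analysis, and it does not show inadequate power.

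**What to change.** Restate the non-inferiority sentence in 9.3.1 on the analysable numbers and name the method. Either of these would do:

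- With 5% loss (475 vs 95 analysable), power is about 87% at a 9% failure rate and above 80% for failure rates up to 11% (unpooled normal approximation).
- With 5% loss (475 vs 95 analysable), exact power of the Wald limit is 93.7% at a 9% failure rate and 83.3% at 12%.

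The second is more informative, because the approximation understates the exact power of the Wald limit; it should be chosen only if that limit is what will be used. Either way, sections 6.9 and 9.5 become true for this comparison and need no edit. The cost is one sentence and, under the first option, a slightly less favourable figure. No additional children are required. Keeping the stated powers under the normal approximation with 5% loss would take about 530 vs 106 randomised, but a 2-point gap does not call for that.

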9.3.2 PHASE II PK TRIAL (PEDI CAP-B)

See **Section 10.1**.

9.4 INTERIM MONITORING & ANALYSES

A Data Monitoring Committee (DMC) Charter will be drawn up that describes the membership of the DMC, relationships with other committees, terms of reference, decision-making processes, and the timing and frequency of interim analyses. The Charter will also contain a description of stopping guidelines: at minimum, these will contain a recommendation for early stopping of the minimum duration group if there is evidence beyond reasonable doubt (Haybittle-Peto stopping rule) that the minimum duration is inferior to the maximum duration on the primary endpoint, with a similar stopping guideline for the comparison of the two oral formulations.

The DMC will meet within 6 months after the trial opens; although the DMC will in general meet annually, the frequency of subsequent meetings will be determined by the DMC and could be more frequent if deemed necessary. The DMC can recommend premature closure or reporting of the trial, or that recruitment to any randomised group be discontinued or modified. Such recommendations would be made if, in the view of the DMC, there is proof beyond reasonable doubt that one of the allocated strategies is better than its comparator in terms of a difference of clinically significant magnitude in a primary outcome.

The guiding statistical criteria for “proof beyond reasonable doubt” is a Haybittle-Peto type rule based on the 99.9% confidence interval in each interim analysis for both superiority and non-inferiority comparisons [54]. See [Section 0](#) for details on DMC membership.

9.5 ANALYSIS PLAN (BRIEF)

The analyses will be described in detail in a full Statistical Analysis Plan. This section briefly summarises the main issues.

The primary analysis population is intention-to-treat, including all randomised children, regardless of treatment received. This corresponds to estimating the impact of the effectiveness of the strategies of stepping down to oral amoxicillin vs co-amoxiclav and varying total duration of antibiotics. However, in secondary analyses we will also use inverse-probability weighting methods to adjust for deviation from randomised strategy, both duration of antibiotic treatment and oral-stepdown, which is a more efficient approach than defining a per-protocol population [55].

As follow-up is short (28 days post-randomisation) lost-to-follow-up should be low, and in each population, the primary comparison between randomised groups will be conducted using binomial regression, reported on the risk difference scale (following the sample size calculation which is based on risk differences). The primary analysis will adjust for the randomisation stratification factors (site and the other factorial randomisation). The primary analysis will be conducted on observed data. Secondary analyses will use multiple imputation with chained estimating equations to impute outcomes for the small (5%) number of expected missing outcomes due to losses to follow-up before 28 days post-randomisation (the sample size calculation in [Section 9.3](#) includes an inflation factor to allow for this). Imputation will be done separately within each randomised group to allow for unknown interactions, and will be based on outcomes and main baseline characteristics as recommended. Duration-response curves will be estimated separately for oral amoxicillin and oral co-amoxiclav randomised groups using fractional polynomials to flexibly model the impact of duration on response following Quartagno et al [33]. A combined model will test whether there is evidence that these duration-response curves vary between co-amoxiclav and amoxicillin using main effects and interactions (i.e. subgroup effects), specifically the following key factors:

- site

- severity
- age
- HIV infection and exposure
- malnutrition (assessed by weight-for-height Z-scores, according to the WHO Growth Standards, and pedal oedema/MUAC)
- initial IV regimen (benzylpenicillin plus gentamicin or ampicillin plus gentamicin, vs benzylpenicillin or ampicillin alone, vs ceftriaxone alone or cefotaxime alone)
- prior oral/intramuscular antibiotics before hospitalisation for the index CAP episode
- baseline CRP (semi-quantitative, 10-40 vs 40-80 vs >80 mg/l)
- chest X-ray features (abnormal vs normal vs uninterpretable vs not done based on any chest X-ray up to and including 72h from admission).

Secondary outcome analyses will similarly use exact tests and binomial regression for binary outcomes, and t-tests and normal linear regression (potentially on transformed data depending on the observed data distribution, adjusted for baseline values) for continuous outcomes. Ranksum tests will be used if there is gross departure from normality that cannot be adequately addressed by data transformation. Adverse events will be summarised by body system.

A Statistical Analysis Plan will be written and approved by the Trial Management Group (TMG), Trial Steering Committee (TSC) and the DMC before the first interim analysis is reviewed by the DMC.

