1 BACKGROUND

1.1 THE ADVERSE IMPACT OF SEVERE PNEUMONIA ON CHILD HEALTH IN AFRICA

Community-acquired pneumonia (CAP) is common and remains associated with substantial morbidity and mortality, especially in lower and middle-income countries (LMIC) [1]. In 2016, 1 per 1000 children younger than 5 years of age was estimated to die due to pneumonia globally [2, 3]. In Africa, pneumonia incidence is estimated at one episode per 3 child-years in young children and severe pneumonia has a mortality of 10-15% [1, 4, 5]. While the proportion of childhood deaths attributable to pneumonia decreased in the 1990s, this has since remained at 18% [6]. Many children with pneumonia in LMIC require inpatient management. In Malawi, 36% of 1-5 year-olds presenting with pneumonia were admitted to hospital and a quarter of these suffered from very severe pneumonia (according to pre-2012 World Health Organisation (WHO) definitions) [5]. In Papua New Guinea the mortality of severe pneumonia requiring hospitalisation was 6%, but another 7% were readmitted with severe pneumonia within 1 month of discharge [7]. In Zambia, the mortality of severe pneumonia managed in hospital was recently estimated at 18% [8]. An overall 5% out-of-hospital mortality has been reported for children discharged in Uganda after inpatient management of an infection, with children of mothers with a lower level of education at much higher risk of death after discharge [9].

The UNICEF and WHO Global Action Plan for prevention and control of pneumonia (GAPP) data [10], indicates that care-seeking of under-fives with pneumonia symptoms in countries represented in PediCAP is relatively high (South Africa 88%, Uganda 80%, Zambia 70%, Zimbabwe 59%). In 2015, high mortality rates from pneumonia were still observed despite improvements since the early 2000s (South Africa 7/1000 live births, Uganda 8.6/1000, Zambia 9.8/1000, and Zimbabwe 10.2/1000) [2]. Correspondingly, acute respiratory infections account for 17% of under-five deaths in South Africa, 16% in Uganda, 14% in Zambia and 15% in Zimbabwe [2]. No robust data are available comparing hospitalisation rates and outcomes across African countries.

The costs associated with inpatient care for severe childhood pneumonia in LMIC are themselves substantial, estimated at up to US\$600 per episode [7]. An early intravenous to oral switch of antibiotics is known to reduce episode costs by around 40% in high-income settings [11], without compromising efficacy.

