6.1.1 BASELINE INFORMATION

At randomisation, medical and relevant social history, including demographics and socioeconomics, documentation of any underlying diseases, mode of delivery, documentation of immunisation status (including taking copies of immunisation records where available), duration of symptoms to date and recent antibiotic exposure, will be recorded. Locator information, including physical address and contact phone numbers will also be collected. Anthropometry will include weight, height/length and mid-upper arm circumference (MUAC) (height/length and MUAC may be collected as soon as practicable post-baseline if not possible to assess at trial entry). Vital signs (respiratory and heart rate, oxygen saturation) and temperature will be measured. Relevant respiratory symptoms and signs will be solicited. Chest X-rays at randomisation will be strongly encouraged where site facilities allow, but are not mandatory. Where possible, and where available, digital copies of all chest X-ray images will be collected.

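### The primary risk difference is valid and adequately powered as stated, but adjusting only for site and the other randomisation forgoes a modest gain in precision from baseline data already collected

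*Protocol*

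**What the plan says.** Section 9.5 says that the primary comparison between randomised groups will be "conducted using binomial regression, reported on the risk difference scale". It then states the adjustment set: "The primary analysis will adjust for the randomisation stratification factors (site and the other factorial randomisation"). On missing outcomes it says "The primary analysis will be conducted on observed data", with multiple imputation as a secondary analysis.

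Section 9.3.1 gives the sample size for the oral drug comparison: "1,000 children randomised 1:1 to oral step-down with amoxicillin vs co-amoxiclav" "provides >80% power to detect a 6% absolute reduction", that is, "from 15% (amoxicillin) to 9% (co-amoxiclav"), with 5% loss to follow-up and two-sided alpha 0.05.

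The trial collects baseline data that could carry prognostic information. Section 6.1.1 lists medical and social history, underlying disease, symptom duration, recent antibiotic exposure, weight, height or length, and MUAC. It adds: "Vital signs (respiratory and heart rate, oxygen saturation) and temperature will be measured". A semi-quantitative CRP is required at screening (Sections 3.2 and 6.5). In Section 9.5 the named baseline factors serve the subgroup and interaction models, and the main baseline characteristics enter the imputation models. None is named for the primary risk difference.

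**The concern.** The outcome is readmission or death within 28 days in children whose baseline risk varies. Section 1.5 describes HIV exposure, malnutrition and severity as risk factors. Section 1.1 cites a Ugandan cohort discharged after treatment for an infection, "with children of mothers with a lower level of education at much higher risk of death after discharge". If variables of this kind predict the outcome, including them in the model for the drug comparison reduces the variance of the estimated treatment effect without recruiting another child.

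The calculated power is only about one percentage point above 80%, so small gains are worth having when they are cheap. What is at stake is efficiency: the width of the interval and a few points of power. Validity, type I error and the choice of estimand are not in question.

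**Working it through.** **Inputs from the protocol (Section 9.3.1).** Risks 0.15 and 0.09; 500 children per arm; 5% loss, so 500 × 0.95 = 475 evaluable per arm; two-sided alpha 0.05.

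**Input not in the protocol.** R², the share of outcome variance that baseline covariates explain beyond site and the other randomisation. I take 0.01 to 0.10 as an assumed range.

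**Step 1: reproduce the stated power.** With pooled variance under the null,

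power = Φ{ [Δ√n − z√(2p̄(1−p̄))] / √[p₁(1−p₁) + p₂(1−p₂)] }

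- Δ√n = 0.06 × √475 = 1.3077
- z√(2p̄(1−p̄)) = 1.96 × √(2 × 0.12 × 0.88) = 0.9007
- √(0.15 × 0.85 + 0.09 × 0.91) = 0.4576
- (1.3077 − 0.9007) / 0.4576 = 0.889, so power = 81.3%

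Variants: 81.5% with unpooled variance; 83.2% with no loss (500 per arm); 78.5% with a continuity correction at 475 per arm. The statement of more than 80% is correct on the usual formula. Without continuity correction, 80% power needs 460 per arm, or 920 in total and 969 after allowing for 5% loss.

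**Step 2: effect of adjustment.** If covariates explain a further share R² of outcome variance, the variance of the risk difference is multiplied by about (1 − R²). This is the same as an effective sample size of 475/(1 − R²) per arm. The interval width is multiplied by √(1 − R²).

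| Incremental R² (assumed) | Effective n per arm | Power | Interval narrower by |
|---|---|---|---|
| 0 | 475 | 81.3% | 0 |
| 0.01 | 480 | 81.7% | 0.5% |
| 0.02 | 485 | 82.1% | 1.0% |
| 0.05 | 500 | 83.2% | 2.5% |
| 0.10 | 528 | 85.2% | 5.1% |

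At R² = 0.05 the effective sample size is 500 per arm, which is exactly what the assumed 5% loss removes.

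**Step 3: what such R² values imply.** With a normal linear predictor on the logit scale and a mean risk of 12%, R² of about 0.03, 0.07 and 0.10 corresponds to a baseline risk model with an AUC of about 0.64, 0.71 and 0.75. These are total R² values. The planned model already contains site, so any prognostic information that site carries is already used and only the increment counts. Reading these AUCs straight into the table therefore gives an upper bound on the gain.

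**The case against.** The strongest objection is that this is a preference and not a defect. Adjusting for the stratification factors is valid and follows the randomisation scheme in Section 9.1. Section 9.5 is labelled brief and defers detail to an SAP, which is not available here and may already add covariates. The gain is small, depends on an assumed R², and is partly captured by site. Most of this stands. The point survives because the protocol lists the adjustment set explicitly, so it is a stated choice and not a gap, and because the improvement is cheap.

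Four stronger readings are tempting, but the document does not support them.

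- **That the protocol treats these variables as key prognostic factors and then ignores them.** The key factors in Section 9.5 are there to test interaction, which is effect modification. Section 1.5 uses the term risk factors when asking whether optimal duration varies. The maternal education finding in Section 1.1 concerns out-of-hospital death after any infection admission, not this endpoint.
- **That adjustment costs nothing.** Section 6.1.1 allows height or length and MUAC to be taken after baseline. Section 3.2 leaves HIV testing to site practice. In the service evaluation (Section 1.4.4) only 4% of children were HIV-infected and 9% HIV-exposed, so HIV may add little. Section 6.1.1 does not say that baseline oxygen saturation is taken on room air, and 65% of surveyed children received oxygen at some point in their stay.
- **That the planned model is liable to non-convergence.** That presumes an identity link. Section 9.5 states only binomial regression reported as a risk difference, and standardisation from a logistic model would fit that wording.
- **That the trial is underpowered.** The stated power is right for the stated assumptions.

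**Conclusion.** The point holds as an optional efficiency improvement of low severity. The planned primary analysis is valid and its stated power reproduces at 81.3%. Its stated adjustment set forgoes some precision that data collected in every child could supply. For an incremental R² of 0.01 to 0.10 the gain is about 0.5 to 4 points of power and an interval about 0.5% to 5% narrower. That range is assumed: the protocol gives no information on how strongly baseline variables predict 28-day readmission or death, and the increment beyond site could lie at the low end. If the SAP already pre-specifies prognostic covariates for the primary model, the point is resolved.

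**What to change.** In the SAP, before the first interim analysis is reviewed:

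- Pre-specify a short covariate list in addition to site and the other randomisation, limited to values measured at or before randomisation in essentially all children. Examples are age, baseline oxygen saturation or a severity measure, weight-for-age, and the semi-quantitative CRP category. Define how saturation recorded on supplemental oxygen is handled.
- Estimate the same marginal risk difference by standardisation from a logistic model, with a delta-method or bootstrap confidence interval.
- Keep the model with site and the other randomisation alone as a sensitivity analysis.
- Include HIV status or exposure, MUAC or weight-for-height only with a stated rule for missing values, because these may be incomplete or collected after baseline.

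The cost is SAP wording, with Section 9.5 aligned at the next amendment. The list must be fixed in advance, and a simple rule is needed for the few missing baseline values. No new data, extra children or change to trial conduct is required.
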